14.4 Tympanometry

Tympanometry results are used for assessment of tube patency and for changes in middle ear condition. Tympanometry will be performed for indicated ears at screening and at each follow-up visit. The number and percentage of ears with tympanogram types A, B or C will be presented for all subjects in the Safety Analysis Set at screening and at the follow-up visits.

14.5 Otoscopic Assessments

Otoscopic examination will be performed for all ears at screening and at each follow-up visit. The number and percentage of indicated ears (at screening) and treated ears (at procedure and follow-up visits) in each Cohort with abnormal findings for the external acoustic meatus or tympanic membrane will be presented for all subjects in the Safety Analysis set at screening, procedure and at the follow-up time visits.

14.6 Cranial Nerve Function

Cranial nerve function physical examination will be performed for all in-office procedure subjects at screening, post-procedure and at the 3-week follow-up visit. The number and percentage of subjects with abnormal findings in the Safety Analysis set for each In-Office Cohort will be presented for the screening, procedure and the 3-week follow-up visit.

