	Enrollment: Up to 422, including 222 pediatric subjects in the pivotal cohort, and up to 100 lead-in OR and up to 100 lead-in in-office subjects.
Safety Measures	
Safety Evaluation will include the following assessments:
 
 • Otoscopic examination for visual inspection of external ear canal, TM condition at all visits (baseline, post-procedure and follow-up visits), with additional assessment of the myringotomy wound and tube at all protocol-specified follow-up visits. • Audiometry to assess hearing at baseline and at the 3-week post-procedure follow-up visit. • Tympanometry to assess tympanic membrane and middle ear conditions at baseline and at all protocol-specified follow-up visits. • Cranial nerve physical exam to assess cranial nerves CN VII (facial) and CN VIII (vestibulocochlear) at baseline, post-procedure and the 3-week post-procedure follow-up visit (in-office lead-in and pivotal subjects only). • Adverse events
Endpoints:	
Primary Endpoints:
 
 • Procedural Success: Proportion of subjects in the pivotal cohort with successful placement of Tusker Medical tympanostomy tubes in all indicated ears in an office procedure • Tube Placement Tolerability: Mean subject-reported pain score following TDS tube placement using the Faces Pain Scale-Revised (FPS-R) (pivotal cohort children ages 5 and older only)
	
Safety Endpoint:
 
 • Safety: Occurrence of adverse events, by subject
	
Secondary Efficacy Endpoints:
 
 • Tube Patency: Tube Patency is the proportion of subjects in the pivotal cohort, in which a Tusker Medical tube was successfully placed, with functionally patent tube(s) in all successfully treated ears at the 3-week post-procedure follow-up visit. • Tube Retention: Tube Retention is the proportion of subjects in the pivotal cohort, in which a Tusker Medical tube(s) was successfully placed, with presence of a Tusker Medical tube across the TM in all successfully treated ears at the 3-week post-procedure follow-up visit. • Anesthesia Effectiveness: Proportion of subjects in the pivotal cohort, who completed iontophoresis for all indicated ears, with adequate

anesthesia for TT placement in all treated ears as determined by physician's evaluation of TM anesthesia prior to tube placement.

Eligibility Criteria:	[REDACTED]

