11.4.3. Cranial Nerve Physical Exam

A standard cranial nerve physical exam will be employed for all subjects enrolled for in-office procedure at screening, after the procedure and at the 3-week post-procedure follow-up visit to identify any potential adverse effects related to the lidocaine iontophoresis anesthesia component of the procedure. [REDACTED]

[REDACTED] Any abnormalities will be recorded at screening, procedure and at the follow-up visit and the subject will be assessed for any adverse events. [REDACTED]

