11.4.4. Otoscopy

An otoscopic exam will be conducted for both ears in all subjects at screening, for all ears intended for treatment at procedure and for all treated at the follow-up visits. The otoscopic examination will be used to visually examine the condition of the external ear canal and TM. Routine ear cleaning may be conducted only to the extent necessary to ensure the tympanic membrane and ear canal are free from matter that may interfere with iontophoretic delivery and to ensure visualization of the tympanic membrane. Ear cleaning at the screening visit is required. Patients who are uncooperative during ear exam and ear cleaning at screening are not eligible study candidates.

The exam will be used to confirm eligibility, to assess the ear canal and TM for changes or adverse effects, and to inspect for residual drug prior to tube placement. In addition, appearance and patency of the tympanostomy tube and appearance of the myringotomy wound will be evaluated post-procedure and at the post-procedure follow-up visits. Presence or absence of middle ear effusion will be assessed.

The screening otoscopic exam may be conducted up to 28 days prior to procedure. Otoscopic examination is considered standard of care for this patient population and may be obtained prior to study informed consent as a screening assessment within 28 days prior to procedure.

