12.0 ASSESSMENT OF SAFETY

12.1. Adverse Events

All reported or observed adverse events that occur during or after the procedure will be recorded. The study Investigator will determine whether an adverse event has occurred, whether life-threatening, serious or non-serious. Pre-existing conditions should not be reported as adverse events unless there has been a worsening in the severity or frequency, which cannot be attributed to natural history or progression of the disease. This definition does not depend on the causal relationship with the device, drug or protocol requirements.

Any change of clinical significance, including vertigo, nausea and vomiting, derived from the protocol evaluations including observations and patient-reported findings will be included as adverse events. Adverse events will also include operative and recovery observation for lead-in procedures conducted in the OR with general anesthesia including, but not limited to, clinically-meaningful vital sign changes, emergence delirium, post-operative nausea, vomiting, disorientation, and complications related to intubation or induction.

All Adverse Events (AEs) will be recorded on dedicated AE case report forms. The event, date of onset, severity, seriousness, duration, treatment, outcome, date or resolution and relationship to device, procedure or drug will be recorded on the AE case report form (CRF). AEs will be categorized by seriousness, relatedness to procedure, investigational drug, or device whether anticipated or unanticipated. All adverse events will be coded using standard terms.

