14.3 Audiometric Assessments

Change in audiometric measurements (shifts) from baseline to the 3-week follow-up visit for subjects in the Safety Analysis Set will be presented using descriptive statistics (mean, SD, median, minimum and maximum). Shifts in air conduction (AC) and bone conduction (BC) hearing thresholds will be reported for each frequency (500, 1000, 2000 and 4000 Hz, and air conduction only at 8000Hz) and for each Cohort on a by-ear basis (treatment ears only). Shifts from baseline to each follow-up visit in air-bone gap (air conduction minus bone conduction) will also be reported for each frequency (500, 1000, 2000 and 4000 Hz) for each Cohort on a by-ear basis. Shifts in air conduction pure tone average (AC PTA), bone conduction PTA (BCA) and air-bone gap averages will be presented for each follow-up time point for each Cohort. For all PTA measurements, the PTA will be calculated by adding the threshold levels in decibels (dB) obtained at each frequency tested divided by number of frequencies tested.

Shift tables for air conduction pure tone averages greater than 15 dB (>15dB) by ear will be calculated, and presented for each Cohort for each follow-up time point.

Degree of hearing loss severity will be defined according to the protocol (slight through profound) and presented by subject for each Cohort and by relationship to study device, procedure or study drug.

Due to the differences in audiometric requirements for children dependent on age, all audiometry results will be presented by subjects less than 4 years of age, greater than 4 years of age, and overall.

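### The cranial nerve and otoscopy safety tables count abnormal findings at each visit, so they cannot separate new or worsened findings from those present at screening

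*SAP*

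**What the plan says.** - Cranial nerves, SAP 14.6: "The number and percentage of subjects with abnormal findings in the Safety Analysis set for each In-Office Cohort will be presented" for screening, procedure and the 3-week visit. The section has no cross-tabulation with screening and does not mention the two nerves separately.
- Otoscopy, SAP 14.5: "The number and percentage of indicated ears (at screening) and treated ears (at procedure and follow-up visits) in each Cohort with abnormal findings" of the ear canal or tympanic membrane (TM), visit by visit.
- Audiometry, SAP 14.3, is handled differently: "Change in audiometric measurements (shifts) from baseline to the 3-week follow-up visit", together with shift tables for air-conduction averages worse by more than 15 dB.
- Purpose of the exams: Protocol 5.0 lists, among the safety measures, "Cranial nerve physical exam to assess cranial nerves CN VII (facial) and CN VIII (vestibulocochlear) at baseline, post-procedure" and at 3 weeks. Protocol 11.4.3 says that this exam is done "to identify any potential adverse effects related to the lidocaine iontophoresis anesthesia component of the procedure". Protocol 11.4.4 uses otoscopy, among other things, "to assess the ear canal and TM for changes or adverse effects".
- Adverse event (AE) route: Protocol 11.4.3 states "Any abnormalities will be recorded at screening, procedure and at the follow-up visit and the subject will be assessed for any adverse events". Protocol 12.1 states "Any change of clinical significance, including vertigo, nausea and vomiting, derived from the protocol evaluations including observations and patient-reported findings will be included" as AEs, and keeps pre-existing conditions out unless they worsen beyond what the natural course of the disease explains. SAP 14.1 tabulates AEs by severity and by relationship to device, procedure and drug. SAP 21.0 lists all eCRF data by subject.

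**The concern.** Both exams are there to detect change after the procedure, but the planned tables report how many are abnormal at each visit. A per-visit percentage mixes findings that persist from screening with findings that are new, and it falls when screening abnormalities resolve. Children enter this trial because of middle-ear disease that a tube is meant to relieve, so some screening abnormalities may well resolve, and new findings could then appear alongside a flat or falling percentage. The trial has one arm, so the child's or ear's own screening exam is the natural comparator for these assessments. The change from indicated to treated ears weakens the otoscopy comparison further, because the rows need not describe the same ears.

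**Working it through.** The documents give no rate, precision target or sample size for these exams, so there is no planned figure to reproduce. The only input taken from them is the pivotal cohort size, 102 + 120 = 222. All other numbers here are assumptions that show how the tables behave.

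**1. What two per-visit counts can reveal.** Let *a* of *N* be abnormal at screening and *b* of the same *N* at follow-up. Then

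new = (*b* − *a*) + resolved,

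with resolved between 0 and *a*. The planned table shows *a* and *b* but not the number resolved. It follows that new lies between max(0, *b* − *a*) and min(*b*, *N* − *a*). The number of new findings exceeds the visible net change by exactly the number resolved, so the offset cannot be larger than *a*.

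| Screening (assumed) | 3 weeks (assumed) | New findings compatible with the table | As a share of those normal at screening |
|---|---|---|---|
| 2/222 (0.9%) | 2/222 (0.9%) | 0 to 2 | 0% to 0.9% of 220 |
| 22/222 (9.9%) | 22/222 (9.9%) | 0 to 22 | 0% to 11.0% of 200 |
| 22/222 (9.9%) | 15/222 (6.8%) | 0 to 15 | 0% to 7.5% of 200 |
| 178/222 (80.2%) | 60/222 (27.0%) | 0 to 44 | 0% to 100% of 44 |

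A shift table would replace each range by the exact number.

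**2. When the direction misleads.** With *p* the share abnormal at screening, *r* the share of these that resolves and *i* the rate of new abnormality among those normal at screening, the expected follow-up share is *p*(1 − *r*) + (1 − *p*)*i*. Take *r* = 80% and *i* = 5%:

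- *p* = 1%: 0.01 × 0.20 + 0.99 × 0.05 = 0.0515. The share rises from 1.0% to about 5.2%, and the roughly 11 new cases (222 × 0.99 × 0.05) stay visible.
- *p* = 10%: 0.10 × 0.20 + 0.90 × 0.05 = 0.065. The share falls from 10.0% to 6.5% although about 10 children (222 × 0.90 × 0.05) are newly abnormal.
- *p* = 80%: 0.80 × 0.20 + 0.20 × 0.05 = 0.17. The share falls from 80% to 17% with about 2 new cases (222 × 0.20 × 0.05).

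The problem is therefore small where screening abnormality is rare and large where it is common.

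**3. Which table is most exposed.** The TM is the likeliest, because eligibility rests on effusion or recurrent otitis (Protocol 11.4.1). That is an inference, since no rate is given. The ear canal is less exposed: otitis externa and damaged canal skin are exclusions (Protocol 10.10). For CN VII and CN VIII the cap is the number abnormal at screening, which is unknown.

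**4. The otoscopy denominator.** The bounds in step 1 need the same units at both visits. SAP 14.5 uses indicated ears first and treated ears later. Any indicated ear that was not treated is in the first row only, so the percentage can move without any ear changing. Children also leave the study once extrusion is confirmed (Protocol 11.10), so the 6- to 24-month rows cover a changing set of ears.

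**The case against.** A reader might infer that these tables let drug or device injury go undetected, for instance that a new facial-nerve finding could not be identified. The documents do not support that. Each abnormality on the cranial nerve exam is recorded and the child is assessed for AEs. Any clinically significant change from a protocol evaluation is an AE. Pre-existing conditions count only if worse, so the AE tables already work as a new-or-worse count, with relationship to device, procedure and drug. The Medical Monitor reviews AEs and their coding periodically (Protocol 12.5), and the subject listings hold the screening and follow-up exams.

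Three further inferences also go beyond the text:

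- Nothing visible says that hearing difficulty from effusion is scored as a CN VIII abnormality.
- The wording of SAP 14.5 on canal or TM findings fits separate rows as well as a pooled count.
- Nothing says that a tube or incision is scored as TM-abnormal; Protocol 5.0 describes wound and tube as an additional assessment.

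Text is redacted in Protocol 11.4.3 and SAP 14.1, so a related rule there cannot be excluded.

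All of this stands and limits the point, but it does not remove it. Entry into the AE tables depends on the investigator judging a change clinically significant and not due to the natural course of the disease, which is a hard call in a diseased ear. The protocol sets numeric thresholds for hearing (worse by more than 15 dB, Protocol 12.4) and for erythema (score of 3 or more, Protocol 11.7.6). No such threshold is visible for cranial nerve or otoscopic findings. Audiometric shifts cover the hearing part of CN VIII, but Protocol 11.4.6 requires testing at both visits only from age 4. Listings allow a case to be found; they do not summarise.

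**Conclusion.** The point holds as a gap in summary reporting. SAP 14.5 and 14.6 cannot separate new or worsened findings from persisting ones, and within those tables resolution can offset new findings. The size cannot be stated from the documents: the offset is at most the number abnormal at screening, which is not given. It is negligible if that number is very small and could be substantial for the TM if abnormal membranes at screening are common, which is an assumption. Clinically significant new findings should still be seen through AE reporting and listings. What remains without a summary is systematic change from baseline that does not depend on the investigator's judgment of significance. No hypothesis test or sample size is affected.

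**What to change.** Keep the per-visit counts and add screening-by-visit shift tables, or the number newly abnormal among those normal at screening.

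- **SAP 14.6:** by subject, at post-procedure and at 3 weeks, with CN VII and CN VIII shown separately where the CRF records them separately. A split by treated side would also depend on CRF capture, which is not visible.
- **SAP 14.5:** by ear, with canal and TM in separate rows. Use the same ears in the denominator at screening and at each later visit. Report the expected appearance of the tube and myringotomy separately from TM abnormality.

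The cost is a few more descriptive tables, programmed from findings that are already recorded at each visit. No new visit or exam is needed.

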15.0 Prior and Concomitant Medications

Prior and concomitant medications including prescription and over-the-counter drugs will be recorded. Medications will be coded to identify the drug class and preferred drug name.

Concomitant medications will include all medications that started on or after the procedure through the final follow-up visit. Prior medications will include all medications that started within 28 days prior and stopped prior to the day of procedure.

Prior and concomitant medication data will be presented in a data listing for safety subjects.

16.0 Other Endpoint Analyses

For continuous and ordinal variables, descriptive statistics will include, at a minimum, the number of observations, mean, standard deviation, median, minimum, and

maximum. For categorical variables, the number and percentage of subjects will be presented.

17.0 Sensitivity Analyses and Handling of Missing Data

The number and proportion of subjects eligible for and compliant with all follow-up examinations will be presented. Subjects who withdraw from the study will be tabulated with the reasons for the withdrawal. Subjects who initiate the procedure, regardless of tolerability outcome or anesthesia effectiveness, will be encouraged to return for all follow-up assessments.

For the Procedural Success primary endpoint, all subjects who initiate iontophoresis are included in the primary analysis of this primary endpoint. Therefore, no missing data analyses for the Procedural Success primary endpoint are planned.

For the Tube Placement Tolerability primary endpoint, all subjects in the pivotal cohort FAS for whom tube placement was successful are included in the primary analysis of this primary endpoint. [REDACTED]

Tube Retention secondary endpoint: Tube Retention is the proportion of subjects in the pivotal cohort FAS, in which a Tusker Medical tube was successfully placed, with presence of a Tusker Medical tube across the tympanic membrane in all successfully treated ears at the 3-week post-procedure follow-up visit. Subjects missing the 3-week follow-up visit will not be included in the Tube Retention secondary analysis.

Tube Patency secondary endpoint: Tube Patency is the proportion of subjects in the pivotal cohort, in which a Tusker Medical tube was successfully placed, with a functionally patent tube in all successfully treated ears at the 3-week post-procedure follow-up visit. Subjects missing the 3-week follow-up visit will not be included in the Tube Patency secondary analysis.

[REDACTED]

[REDACTED]

[REDACTED]

[REDACTED]

Anesthesia Effectiveness secondary endpoint: Anesthesia Effectiveness is the proportion of subjects in the pivotal cohort FAS, who completed iontophoresis for all indicated ears, with adequate anesthesia for tympanostomy tube placement in all treated ears as determined by physician's evaluation of TM anesthesia prior to tube placement. Subjects who complete iontophoresis but do not complete TM tap assessment for all indicated ears will be counted as failures. [REDACTED]

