11.7.10. Unsuccessful Procedures

If the in-office procedure is not a success and the physician refers the subject for traditional OR TT placement, the Investigator will document the OR procedure TT placement success. Reasons for any OR procedural failures (of TT placement) will be documented. The OR procedure must take place within 2 months of the first in-office procedure. The subject must complete a post-procedure follow-up visit after the failed in-office procedure, at the protocol specified 3-week follow-up visit, or earlier if the OR procedure is planned prior to the 3-week visit. If no Tusker tube was placed, no additional follow-up visit is required following the subsequent procedure. If a Tusker tube was placed, the subject should follow the protocol-specified follow-up visit schedule to assess safety of the Tusker tube.

[REDACTED]

11.9.3-Week Post-Procedure Follow-Up Visit (+/- 7 Days)

[figure not shown]
1. All subjects are required to return for the 3-week post-procedure follow-up visit.
2. An otoscopic examination will be used to visually examine the condition of the external ear canal, TM, myringotomy, tube retention and patency.
3. The subject will complete the audiology and tympanometry, and cranial nerve physical exam (for in-office subjects only).
4. Subjects will be evaluated for any adverse events, and changes in concomitant medications will be recorded.

11.10. 6, 12, 18 and 24-month Post-Procedure Follow-Up Visits (+/- 28 days)

1. All subjects are required to return for additional follow-up visits through confirmation of tube extrusion (both ears if bilateral tube placement).
2. An otoscopic examination will be used to visually examine the condition of the external ear canal, TM, myringotomy, tube retention and patency.
3. The subject will complete tympanometry. If audiology is indicated, the study will collect audiometric data however there is no study requirement for audiology or audiology method for follow-up visits subsequent to the 3-week visit.
4. Subjects will be evaluated for any adverse events, and changes in concomitant medications will be recorded.
5. The subject will be exited from the study following confirmation of tube extrusion or completion of the 24 month visit if tube remains in place.

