13.4. Secondary Efficacy Endpoint Analyses

Secondary endpoints will be tested on the 102 older children upon successful achievement of the primary endpoints. If the 102 older children pass the test, a gatekeeper design will be employed and the secondary endpoints will be tested on the full pivotal cohort once enrolled (102 older children plus 120 younger children). The secondary endpoints (Tube Patency, Tube Retention and Anesthesia Effectiveness) are functions of the tube and iontophoresis device performance and are not anticipated to vary by subject age. Therefore, testing the secondary endpoints on the full (pooled) pivotal cohort is appropriate.

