11.2 Tube Retention

Tube Retention is the proportion of subjects in the pivotal cohort FAS, in which a Tusker Medical tube was successfully placed, with presence of a Tusker Medical tube across the tympanic membrane in all successfully treated ears at the 3-week post-procedure follow-up visit.

The statistical test for the pivotal cohort Tube Retention secondary endpoint is a hypothesis test for the proportion of subjects with a Tusker tube at the 3-week follow-up visit against a Tube Retention performance goal. A mid-P method for a single proportion will be used to test

$H_0: p \leq 88\%$ vs. $H_a: p > 88\%$

This endpoint will be considered met if the p-value from the test is less than 0.025.

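### The Tube Retention and Tube Patency tests drop every child who misses the 3-week visit, including any whose tube loss before then is already documented; those children should count as failures.

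*SAP*

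**What the plan says.** SAP 11.2 defines Tube Retention among Full Analysis Set children in whom a tube was placed. Success is judged "with presence of a Tusker Medical tube across the tympanic membrane in all successfully treated ears at the 3-week post-procedure follow-up visit". The null rate is 88%. The analysis is described by "A mid-P method for a single proportion will be used to test", and "This endpoint will be considered met if the p-value from the test is less than 0.025". SAP 11.1 sets up Tube Patency in the same way against 80%.

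Protocol 13.4 gives the order of testing: "Secondary endpoints will be tested on the 102 older children upon successful achievement of the primary endpoints", and, if that succeeds, "the secondary endpoints will be tested on the full pivotal cohort once enrolled (102 older children plus 120 younger children".

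SAP 17.0 gives the missing-visit rule for each endpoint: "Subjects missing the 3-week follow-up visit will not be included in the Tube Retention secondary analysis" and "Subjects missing the 3-week follow-up visit will not be included in the Tube Patency secondary analysis". Neither sentence carries a condition. Protocol 13.8 refers missing data to the SAP and offers no other rule.

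The trial has other places where tube status can be recorded. Protocol 12.1 has adverse events recorded during and after the procedure. Under Protocol 11.9 and 11.10, otoscopy at week 3 and again at 6, 12, 18 and 24 months is used to "examine the condition of the external ear canal, TM, myringotomy, tube retention and patency", continuing until extrusion is confirmed.

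**The concern.** The exclusion depends on attendance alone and ignores what is known about the tube. Take a child whose tube is recorded as out on day 10 and who then does not attend. The endpoint requires a tube across the membrane in all successfully treated ears at week 3, so the outcome is settled: failure. SAP 17.0 nevertheless removes the child from numerator and denominator. The same child would count as a failure if the family had kept the appointment.

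Patency follows directly, because a tube that has gone is not patent.

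At stake is whether two hypothesis-tested secondary endpoints are met. Both are single proportions against fixed goals, and at these sample sizes the pass boundary is only a few failures wide.

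**Working it through.** The visible text states no sample size, power or attrition figure for Tube Retention, so there is no plan figure to reproduce. The counts below are assumptions chosen to show sensitivity.

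**Inputs from the documents.** Null rate p0 = 0.88 and threshold 0.025 (SAP 11.2), one-sided by the form of the hypotheses. Group sizes are 102 older children and 102 + 120 = 222 in all (Protocol 13.4). These are upper limits on the denominator, because only children with a tube placed count.

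**Formula.** For x retained out of n, mid-P = P(X > x) + 0.5 × P(X = x), with X binomial(n, 0.88).

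**Pass boundary.** n = 102 needs 96 (at most 6 failures; mid-P 0.0223). n = 222 needs 205 (at most 17 failures; 0.0191). If tubes were placed in only about 68%, the denominators fall to about 70 and 151, needing 67 (at most 3 failures) and 141 (at most 10).

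**Documented failures dropped (SAP rule) or kept:**

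| Assumed children with a tube | Documented failures absent at week 3 | Dropped | Kept |
|---|---|---|---|
| 102 | 1 | 95/101: 0.0140 + 0.5 × 0.0201 = 0.0241, met | 95/102: 0.0317 + 0.5 × 0.0352 = 0.0493, not met |
| 222 | 1 | 204/221: 0.0146 + 0.5 × 0.0112 = 0.0202, met | 204/222: 0.0244 + 0.5 × 0.0166 = 0.0327, not met |
| 222 | 3 | 202/219: 0.0225, met | 202/222: 0.0822, not met |
| 189 (85% of 222) | 1 | 174/188: 0.0227, met | 174/189: 0.0380, not met |
| 70 (about 68% of 102) | 1 | 66/69: 0.0178, met | 66/70: 0.0458, not met |
| 183 | 3 | 170/180: 0.0020, met | 170/183: 0.0163, met |

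The first five rows sit at or next to the boundary by construction. The last starts further away and survives three restored failures, though 170 is also the smallest passing count at n = 183.

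**Does exclusion by itself inflate the error rate?** Take a true retention rate of 88% and let failures and successes miss the visit at different assumed rates. The probability of meeting the goal is then:

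| Failures missing / successes missing | N = 102 | N = 222 |
|---|---|---|
| 0% / 0% | 0.032 | 0.024 |
| 5% / 5% | 0.021 | 0.025 |
| 10% / 2% | 0.036 | 0.053 |
| 20% / 5% | 0.065 | 0.112 |

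Equal missingness produces no inflation. Inflation appears only when failures miss the visit more often than successes. The table excludes all absent failures, documented or not, so scoring only the documented ones would recover only part of the difference.

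**The case against.** The strongest reply is that the affected group may be nearly empty. Protocol Table 4 has no visit between the procedure and week 3, so the scheduled place to notice an early loss is the visit that was missed. The visible text does not say that extrusion is recorded as an adverse event or on an interim form. A loss first seen at 6 months does not show the status at week 3. The visit is required of all subjects, has a 7-day margin either side (Protocol 11.9), and loss to follow-up can be declared only after three contact attempts (Protocol 15.1). All of this stands. It limits the size of the problem but does not justify the rule where a loss is documented.

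A reader might infer four stronger things that the documents do not support.

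- *The rule tilts retention toward the goal.* It also drops children later seen with their tubes in place, which works the other way. Nothing in the documents says that children with failures attend less often.
- *The SAP has no sensitivity analysis for this.* Redacted blocks follow the patency paragraph in SAP 17.0, so absence cannot be asserted. A sensitivity analysis there would not, however, alter the stated rule for the tested analysis.
- *SAP 17.0 contradicts itself because an incomplete eardrum tap counts as failure for Anesthesia Effectiveness.* The tap is a same-day step, and failing to complete it may reflect the child's response to the procedure. A visit missed weeks later is a different kind of missing data.
- *Every absent child should be a failure in the main test.* A tube in place at week 3, lost at month 4 and first checked at month 6 would be scored wrongly. That worst-case assumption belongs in a sensitivity analysis.

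**Conclusion.** The point holds in a limited form. As written, SAP 17.0 removes children whose failure is already documented, against the endpoint definition in SAP 11.1 and 11.2. One such child can reverse a retention result at the boundary in either the older group or the full cohort. A result a few failures clear of the boundary would not change. These examples rest on assumed numbers of children with tubes, of missed visits and of documented losses, none of which the documents give. The direction of any net bias is not established. This is a minor correction to two secondary endpoints and does not touch the primary analyses.

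**What to change.** In SAP 17.0, count a child with extrusion, removal or replacement in any treated ear, documented before the 3-week window closes (day 21 + 7 = day 28), as a failure for both Tube Retention and Tube Patency, whether or not the visit took place. Name replacement explicitly, since the definition asks only for the presence of a Tusker tube.

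Unless the redacted text already provides it, add a sensitivity analysis for retention: credit as retained any child whose original tubes are seen in all treated ears at a later visit, and count all undetermined children as not retained. Do not credit later-seen tubes while still excluding the undetermined. Later visits can confirm retention at week 3 but cannot date a loss first seen then, so that combination would bias retention upward. Do not carry the credit to patency, because a tube patent later was not necessarily patent at week 3.

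The cost is SAP wording, with no new visits. The change to the main test can only add failures, so the retention and patency figures may become slightly less favourable.
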